## **Appendices**

## Appendix 1: Study Glossary

Term	Definition
AE	Adverse event
CHA	Complementary Health Approach
CI	Confidence interval
DCT	Data collection tools
HIPAA	Health Insurance Portability and Accountability Act of 1996
IRB	Institutional Review Board
NCCIH	National Center for Complementary and Integrative Health
NIH	National Institutes of Health
OSU	The Ohio State University
PCRC	Palliative Care Research Cooperative Group
PROMIS	Patient Reported Outcomes Measurement Information System
PTES	Perceived Treatment Efficacy Scale
PI	Principal Investigator
QOL	Quality of life
RCT	Randomized controlled trial
SAE	Serious adverse event
T0	Enrollment
T1	Week 4
T2	Week 8

## Appendix 2: Study Schema

## **Appendix 3: Measures**

**Demographic Data Form**

ID # \_\_\_\_\_

**Adolescent:****Where was the adolescent consented:** Inpatient / outpatient clinic / home / other (circle one)**Has the adolescent been hospitalized in the last month? Y/N (circle one)**

If yes, discharge date: \_\_\_\_\_

**Age in years:** \_\_\_\_\_ **Birthdate:** \_\_\_\_\_**Sex:** Unknown     Male     Female     Not specified/Decline to answer**Race:**

	American Indian or Alaska Native		Native Hawaiian or Pacific Islander
	Asian		White
	Black or African American		Unknown

**Ethnicity:** Hispanic or Latino     Not Hispanic or Latino     Unknown**Religion:**

 Amish	 Jewish	 None
 Buddhist	 Catholic	 Other: _____
 Hindu	 Protestant/Christian*	 Decline to Answer
 Muslim	(*includes Baptist, Presbyterian, Methodist, Lutheran, Episcopalian, Church of Christ, Pentecostal/Foursquare, Christian Science, Quaker, Unitarian, etc.)	
 Spiritual but not religious		

Primary diagnosis that resulted in palliative or hospice referral

Is the child developmentally delayed? Yes \_\_\_\_\_ No \_\_\_\_\_

(as defined by parent report & PPC provider opinion)

If yes, Diagnosis: \_\_\_\_\_ ICD-10: \_\_\_\_\_

Is the adolescent receiving palliative care? Yes \_\_\_\_\_ No \_\_\_\_\_

Date referred to palliative care: \_\_\_\_\_ / \_\_\_\_\_ / \_\_\_\_\_

Is the adolescent receiving hospice care? Yes \_\_\_\_\_ No \_\_\_\_\_

Where is care provided: \_\_\_\_\_

Date referred to hospice care: \_\_\_\_\_ / \_\_\_\_\_ / \_\_\_\_\_

**Parent/Legal Guardian:**

Age \_\_\_\_\_ Sex \_\_\_\_\_

**Race:**

 American Indian or Alaska Native	 Native Hawaiian or Pacific Islander
 Asian	 White
 Black or African American	 Unknown

**Ethnicity:**

Hispanic or Latino  Not Hispanic or Latino  Unknown

**Current Marital Status:**

 Single	 Widowed
 Married	 Living with romantic partner
 Divorced	 Decline to answer

**Employment:**

 Part Time	 Family Medical Leave
 Full Time	 Homemaker
 Seasonal/occasional	 Retired
 Unemployed	 Decline to answer

**Educational Level:**

 Less than high school	 Bachelor's Degree
 High school	 Master's Degree
 Some college	 Doctoral Degree
 Associates Degree	 Decline to answer

Total number of people living in the household: \_\_\_\_\_

**Total Family Income (yearly):**

 < \$10,000	 \$60,000-79,999
 \$10,000-19,999	 >\$80,000
 \$20,000-39,999	 Decline to answer
 \$40,000-59,999	

**Religion:**

 Amish	 Jewish	 None
 Buddhist	 Catholic	 Other: _____
 Hindu	 Protestant/Christian*	 Decline to Answer
 Muslim	(includes Baptist, Presbyterian, Methodist, Lutheran, Episcopalian, Church of Christ, Pentecostal/Foursquare, Christian Science, Quaker, Unitarian, etc.)	
 Spiritual but not religious		

## Pediatric Global Health 7+2

**Please respond to each question or statement by marking one box per row.**

		Excellent	Very Good	Good	Fair	Poor
Global01R1	In general, would you say your health is:.....	 5	 4	 3	 2	 1
Global02R1	In general, would you say your quality of life is:.....	 5	 4	 3	 2	 1
Global03R1	In general, how would you rate your physical health? .....	 5	 4	 3	 2	 1
Global04R1	In general, how would you rate your mental health, including your mood and your ability to think? .....	 5	 4	 3	 2	 1
PedGlobal2R1	How often do you feel really sad? .....	 5	 4	 3	 2	 1
PedGlobal5R1	How often do you have fun with friends? .....	 5	 4	 3	 2	 1
PedGlobal6R1	How often do your parents listen to your ideas? .....	 5	 4	 3	 2	 1
In the past 7 days...						
2876R1r	I got tired easily .....	 1	 2	 3	 4	 5
3793R1r	I had trouble sleeping when I had pain.....	 1	 2	 3	 4	 5

## Parent Proxy Global Health 7+2

**Please respond to each question or statement by marking one box per row.**

		Excellent	Very Good	Good	Fair	Poor
Global01_PXR1	In general, would you say your child's health is:.....	 5	 4	 3	 2	 1
Global02_PXR1	In general, would you say your child's quality of life is:.....	 5	 4	 3	 2	 1
Global03_PXR1	In general, how would you rate your child's physical health? .....	 5	 4	 3	 2	 1
Global04_PXR1	In general, how would you rate your child's mental health, including mood and ability to think? .....	 5	 4	 3	 2	 1
		Never	Rarely	Sometimes	Often	Always
PedGlobal2_PXR1	How often does your child feel really sad? .....	 5	 4	 3	 2	 1
		Always	Often	Sometimes	Rarely	Never
PedGlobal5_PXR1	How often does your child have fun with friends? .....	 5	 4	 3	 2	 1
PedGlobal6_PXR1	How often does your child feel that you listen to his or her ideas? .....	 5	 4	 3	 2	 1
	In the past 7 days...	Never	Almost Never	Sometimes	Often	Almost Always
Pf4fatigue3r	My child got tired easily .....	 1	 2	 3	 4	 5
Pf2pain5r	My child had trouble sleeping when he/she had pain.....	 1	 2	 3	 4	 5

## Pediatric Pain Interference

Please respond to each item by marking one box per row.

In the past 7 days. . . .		Never	Almost Never	Sometimes	Often	Almost Always
		0	1	2	3	4
1698bR1	I felt angry when I had pain.					
2035R1	I had trouble doing schoolwork when I had pain.					
3793R1	I had trouble sleeping when I had pain.					
9004	It was hard for me to pay attention when I had pain.					
2045R1	It was hard for me to run when I had pain.					
2049R1	It was hard for me to walk one block when I had pain.					
1703R1	It was hard to have fun when I had pain.					
2180R1	It was hard to stay standing when I had pain.					
3582R1	I hurt a lot.					
9009	I hurt all over my body.					
2032R1	I missed school when I had pain.					
9007	It was hard for me to remember things when I had pain.					
1701R1	It was hard to get along with other people when I had pain.					

## Pain Interference

**Please respond to each question or statement by marking one box per row.**

	In the past 7 days...	Never	Almost Never	Sometimes	Often	Almost Always
Pf2pain5	My child had trouble sleeping when he/she had pain .....	 0	 1	 2	 3	 4
Pf3pain7	My child felt angry when he/she had pain .	 0	 1	 2	 3	 4
Pf2pain2	My child had trouble doing schoolwork when he/she had pain .....	 0	 1	 2	 3	 4
Pf3pain2	It was hard for my child to pay attention when he/she had pain .....	 0	 1	 2	 3	 4
Pf2pain4	It was hard for my child to run when he/she had pain .....	 0	 1	 2	 3	 4
Pf1pain4	It was hard for my child to walk one block when he/she had pain .....	 0	 1	 2	 3	 4
Pf3pain4	It was hard for my child to have fun when he/she had pain .....	 0	 1	 2	 3	 4
Pf4pain6	It was hard for my child to stay standing when he/she had pain .....	 0	 1	 2	 3	 4
Pf4pain2	It was hard for my child to remember things when he/she had pain.....	 0	 1	 2	 3	 4
Pf4pain4	It was hard for my child to get along with other people when he/she had pain .....	 0	 1	 2	 3	 4
Pf4pain1	My child hurt a lot.....	 0	 1	 2	 3	 4
Pf3pain6	My child hurt all over his/her body .....	 0	 1	 2	 3	 4
Pf4pain5	My child missed school when he/she had pain .....	 0	 1	 2	 3	 4

# PROMIS-29 Profile v2.0

Please respond to each question or statement by marking one box per row.

Physical Function		Without any difficulty	With a little difficulty	With some difficulty	With much difficulty	Unable to do
1	Are you able to do chores such as vacuuming or yard work? .....					
2	Are you able to go up and down stairs at a normal pace? .....					
3	Are you able to go for a walk of at least 15 minutes? .....					
4	Are you able to run errands and shop? .....					
Anxiety		Never	Rarely	Sometimes	Often	Always
5	I felt fearful.....					
6	I found it hard to focus on anything other than my anxiety .....					
7	My worries overwhelmed me.....					
8	I felt uneasy .....					
Depression		Never	Rarely	Sometimes	Often	Always
9	I felt worthless .....					
10	I felt helpless.....					
11	I felt depressed.....					
12	I felt hopeless.....					
Fatigue		Not at all	A little bit	Somewhat	Quite a bit	Very much
13	I feel fatigued .....					
14	I have trouble starting things because I am tired.....					

## PROMIS-29 Profile v2.0

Fatigue						
In the past 7 days...		Not at all	A little bit	Somewhat	Quite a bit	Very much
15	How run-down did you feel on average? ...					
16	How fatigued were you on average? .....					
Sleep Disturbance						
In the past 7 days...		Very poor	Poor	Fair	Good	Very good
17	My sleep quality was.....					
In the past 7 days...		Not at all	A little bit	Somewhat	Quite a bit	Very much
18	My sleep was refreshing.....					
19	I had a problem with my sleep .....					
20	I had difficulty falling asleep .....					
Ability to Participate in Social Roles and Activities						
		Never	Rarely	Sometimes	Usually	Always
21	I have trouble doing all of my regular leisure activities with others					
22	I have trouble doing all of the family activities that I want to do .....					
23	I have trouble doing all of my usual work (include work at home) .....					
24	I have trouble doing all of the activities with friends that I want to do .....					
Pain Interference						
In the past 7 days...		Not at all	A little bit	Somewhat	Quite a bit	Very much
25	How much did pain interfere with your day to day activities? .....					
26	How much did pain interfere with work around the home? .....					
27	How much did pain interfere with your ability to participate in social activities? .....					
28	How much did pain interfere with your household chores? .....					

## PROMIS-29 Profile v2.0

### Pain Intensity

In the past 7 days...

29

How would you rate your pain on average?.....

										
0	1	2	3	4	5	6	7	8	9	10
No pain										
Worst imaginable pain										

## INTERVIEW GUIDE

### Teaching Parents Reiki for Their Adolescents Receiving Palliative Care

Interviews with parents can take place in a setting of their choosing. Assure that the risk for interruptions is minimized.

#### Introductory Comments:

We value your opinions as parents who have been engaged in symptom management with your child. We'd like to obtain some feedback about using REIKI therapy to help with those symptoms. All opinions and information shared here will be confidential and your participation is anonymous. We don't share your names or your opinions by name or attach any identifying information to the transcript of this session. I will be recording this session if it's OK with you. This is just to make sure I get an accurate record of your answers. We will listen to the recording and transcribe the words into text on the computer. No one will have access to your responses except study personnel. Do we have your permission to proceed with the recording?

I have a series of questions I want to cover and these are open-ended questions so think of this more like a conversation than a questionnaire or a survey, and of course you are free to refuse to answer any questions or to stop the interview at any point. But, really, feel free to raise any issues that you think are important or central to some of the things that we discuss today. We really designed the questions to try to address some of the areas we think are key to understanding how you used REIKI with your child.

Also, I'm going to be using the word "child" even though \_\_\_\_\_ is an adolescent. Is that okay with you?

Before we get started, do you have any questions or concerns?

1. Tell me a little about your child.
  - a. What kinds of symptoms are most distressing for your child?
  - b. Can you describe how you manage those symptoms? Before REIKI? Please describe a typical day before the REIKI training.
2. Tell me about the REIKI training.
  - a. How long did it take to learn?
  - b. How difficult was it for you to learn? What about the practice – was it enough to make you feel comfortable with your ability to administer REIKI to your child?
  - c. Was there anything about the training that you think should be changed for other parents?
3. So, you have had about 4 weeks to use REIKI with your child to help managing their symptoms.
  - a. Can you describe how you typically use it?
  - b. How often do you use it?
  - c. How do you make the decision to use it?
  - d. Would there be a situation that you might not use REIKI?
  - e. Were there any particular symptoms that you felt were easier to manage using REIKI?
  - f. Were there any symptoms that it just didn't work for?
  - g. Can you describe a situation where using REIKI was particularly effective?

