### **3.2.1 Study events description**

Dyads will be in the study for a total of nine weeks from enrollment to the follow-up visit. Screening occurs at least weekly and prior to enrollment. Enrollment and initial study measure completion, including first hair sample collection from both parent and adolescent, will occur at the beginning of Week 0. Parents will fill out the Medication Log during Week 0 in order to have a baseline of pain and anxiety medications before study intervention begins. The parent will receive Reiki training, a poster with suggested hand positions and a commercially-available book about Reiki in the home on the first day of Week 1. A visit window is defined as a week (7days) -1/+3 days from the initial Reiki training. During Week 2 the parent will receive a Reiki booster session with a repeat of the training and may ask questions. The parent will administer at least 5 times per week for at least 10 minutes each session. During weeks 1-4, the parent will collect saliva samples for themselves and their adolescent before and after any two Reiki sessions as long as they are collected on two separate days. At the end of Week 4, measures will be repeated either in person or by phone. During Week 8, measures will be repeated, the second hair sample obtained from both parent and adolescent, and the parent will participate in a qualitative interview. The qualitative interview will be administered in person by trained OSU College of Nursing

study staff as part of the interview session. Interviews will be audio recorded using a hand-held audio recording device. Audio recordings will be transcribed verbatim. Audio recording is voluntary and participants can choose to not have their interview recorded and still be a part of the study. See Appendix 2 for schema.

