## **3.3 Interventions**

This is a one-group feasibility study. There is only one intervention group. The Overall-Study PI and Local PI will recruit professional Reiki practitioners who are trained at Level 3 or Master Level and have prior experience working with families and children. A Reiki Master will perform the initial teaching and instruct the parent how to perform a simple 15-minute Reiki session. Parents will complete a return demonstration using light touch with their adolescent. The parent will receive an introductory book on Reiki, an informational article, and a poster showing hand positions for their reference as well as the intervention log to record sessions. The initial teaching session will take about 1.5 hours with breaks. The initial teaching session will be conducted by a Reiki Master and will mark the beginning of Week 1. A Reiki practitioner (Master or Level 3) will provide a shorter "booster" session the following week to review techniques with the parent and answer questions. This session will last 45 minutes with breaks. The "booster" session will count as one day for that week. Parents will be asked

to complete a minimum of 15 minutes of Reiki with their adolescent at least five days per week for the four-week intervention period. Parents will receive a phone call from the research coordinator once per week during weeks three and four to check in with them and ask if they have any questions or problems with the intervention and will refer to a Reiki practitioner if needed.

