## 4 Statistics and Data Handling

### 4.1 Statistical considerations

Primary outcomes (Aims 1): Feasibility will be examined by computing the proportion of approached subjects enrolled in the study, the proportion of subjects who complete Reiki training, and the proportion of enrolled subjects' who completed data collection. Qualitative data will be analyzed using a basic qualitative descriptive approach. Qualitative data (audio recorded interviews and field notes) will be transcribed verbatim, checked for accuracy, imported into Atlas.TI for data management, and analyzed. Portions of text are labeled or coded with terms that are descriptive of the user opinions and observations. Codes will be identified and defined in an iterative process by investigators independently coding the data and arriving at agreement in discussion/review. Codes are sorted and categorized into themes, which will be discussed in research meetings. We will use mixed methods to triangulate the qualitative and quantitative data to produce a more accurate picture of parental beliefs and experiences. These results will be used to refine procedures for future, larger studies. Qualitative results will be triangulated with quantitative results to answer questions of feasibility. Qualitative results will also be examined to explore the parents' confidence in delivering Reiki and beliefs in their ability to help their adolescent (Aim 3).

Secondary outcomes (Aim 2): Descriptive statistics will be used to check data distribution, identify outliers, examine the balance in baseline measurements, and report outcome measures (e.g. pain) at each time point. Trend plot will be used to visualize the trend of change over time. Pair-wise comparisons will be conducted to test the difference in the change in outcome measures (T0 versus T1, T1 versus T2, T0 versus T2) using two sample t-tests. We will not adjust for multiple comparisons to avoid further reduction of power. Mixed effect modeling for repeated measures will be used to examine the trajectories of treatment effect over time, adjusting for within-patient clustering from repeated measures and possible confounders.

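### The interview guide's lead-in says about 4 weeks of Reiki, but the interview is in Week 8, about 7 to 8 weeks after training, so answers on use may describe different weeks

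*Combined protocol and SAP*

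**What the plan says.** **Timing.** Section 3.3 fixes the start of the clock: "The initial teaching session will be conducted by a Reiki Master and will mark the beginning of Week 1". The same section asks parents to give Reiki "at least five days per week for the four-week intervention period". Section 3.2.1 states that in Week 8 "the parent will participate in a qualitative interview". Table 1 agrees, listing the parent's experience of providing Reiki at T2 only, and section 3.2.2 and the glossary define T2 as Week 8. Section 3.2.1 also gives a window: "A visit window is defined as a week (7days) -1/+3 days from the initial Reiki training".

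**Script.** The guide introduces question 3 with "So, you have had about 4 weeks to use REIKI with your child to help managing their symptoms". Items 3a to 3c then ask, in the present tense, how the parent typically uses Reiki, how often, and how the decision to use it is made. Item 3d is conditional. Items 3e to 3g look back on symptoms and situations in which Reiki did or did not help. None of the items names the weeks it concerns.

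**Other record of use.** Table 1 has the Parent Intervention Log completed in Weeks 1-4. Its entries are dated sessions. No log is planned for Weeks 5-8.

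**Analysis.** Section 4.1 says: "Qualitative results will be triangulated with quantitative results to answer questions of feasibility". It does not name the log as the quantitative partner.

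**The concern.** The lead-in states a duration that is not the elapsed time at the visit where the script is read out. A parent hearing it in Week 8 can take it in two ways. It may name the four intervention weeks, or it may simply be a wrong count of the time up to today. The present-tense items that follow pull toward today. Neither the parent nor the analyst coding the transcript is told which reading applies.

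Section 3.2 makes the parent interviews part of how feasibility and acceptability, the primary outcome, are judged, and section 4.1.1 puts the emphasis on Aims 1 and 3. None of the three proportions in section 4.1 measures how much Reiki was delivered, so evidence on actual use comes from the log and from these questions. Under section 3.2.3, a log that is blank or has fewer than five entries for the week may be completed afterwards when staff ask. A parent's account with a clear period would therefore be a useful cross-check. With 12 dyads, a few answers of unknown period could shift a theme, and the period cannot be recovered reliably once the interview is over.

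**Working it through.** **Inputs**
- Training: first day of Week 1 (sections 3.2.1 and 3.3). Call it day 0.
- Interview: Week 8 (section 3.2.1, Table 1).
- Intervention and log: Weeks 1-4 (section 3.3, Table 1).
- Window: -1/+3 days (section 3.2.1). It is not clear that it applies to the Week 8 visit, so both results are shown.

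**Formula.** Week *w* runs from day 7 × (*w* - 1) to day 7 × (*w* - 1) + 6.

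**The script's own figure**
- Weeks 1-4 contain 4 weeks, or 4 × 7 = 28 days. This matches the script.
- An interview at the close of Week 4 (T1) would fall 28 / 7 = 4.0 weeks after training. This also matches.

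The scripted figure is therefore right as the length of the intervention, or as elapsed time at T1.

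**Elapsed time at the scheduled interview**
- Week 8 starts on day 7 × (8 - 1) = 49 and ends on day 49 + 6 = 55.
- In weeks: 49 / 7 = 7.0 to 55 / 7 = 7.9.
- With the window: day 49 - 1 = 48 to day 55 + 3 = 58, or 48 / 7 = 6.9 to 58 / 7 = 8.3 weeks.

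**Time with no log before the interview**
- 49 - 28 = 21 days to 55 - 28 = 27 days, or 3.0 to 3.9 weeks.
- With the window: 48 - 28 = 20 to 58 - 28 = 30 days, or 2.9 to 4.3 weeks.

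**Consistency of the schedule.** Weeks 0 to 8 inclusive make 9 weeks, the stated total. T1 to T2 is 8 - 4 = 4 weeks, the stated follow-up. The schedule agrees with itself, and the script is the outlier.

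**What the ambiguity does (hypothetical parents).** Two parents each log five days a week in Weeks 1-4, or 5 × 4 = 20 session days. One then stops and the other continues. Asked in Week 8 how often they use Reiki, the first could truthfully say five times a week (meaning the study weeks) or not at all (meaning now). The second gives one answer under either reading. The logs are identical, and the transcripts may differ only because of the period each parent had in mind.

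**The case against.** The strongest reply is that this is a loose phrase in an open-ended interview. The four weeks in the script equal the length of the intervention, so the lead-in can be read as pointing at the logged weeks. Only three of the seven items under it are in the present tense, and the guide's introduction speaks of use in the past. Trained staff conduct the interview as a conversation and can probe. Section 3.2 describes its subject as the teaching, the usefulness of Reiki and the study as a whole, not frequency of use, which has its own source in the log.

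Much of this stands. It confines the problem to 3a to 3c and makes it one of interpretation. It does not remove it. The wording of the lead-in runs up to the present, the present-tense items reinforce that, and the guide does not prompt the interviewer to settle the period.

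A reader might also infer more than the documents support:
- *That the answers cannot be compared with the log.* Log entries are dated, so any answer clearly about Weeks 1-4 can be compared.
- *That about half of the Reiki being described is unlogged.* The documents do not say whether parents continue after Week 4. Elapsed time is not exposure.
- *That the plan matches interview answers to log entries.* Section 4.1 refers only to quantitative results in general.
- *That question 1b is flawed in the same way*, because "Please describe a typical day before the REIKI training" is asked at least 48 days after training, and that it should move to enrollment. Looking back in this way is ordinary in an end-of-study interview, and baseline is already recorded through the PROMIS measures at T0 and the Medication Log in Week 0. Moving it would add a recorded contact and is a matter of preference.

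**Conclusion.** The concern holds in a limited form. The guide's stated 4 weeks and the scheduled interview at about 7 to 8 weeks after training do not agree. Together with present-tense wording and no recall period, this leaves the weeks described in 3a to 3c uncertain. Answers may concern logged weeks, unlogged weeks or both. How many would be affected cannot be estimated, because it depends on whether parents use Reiki in Weeks 5-8 and how they hear the question.

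The effect is on reading reported use alongside the log, within the qualitative part of the primary outcome. The proportions enrolled, trained and completing data collection do not change, and neither does the sample size of 12 dyads. The conclusion assumes that the interview takes place in Week 8 as scheduled and that the guide is used as printed. It is worth correcting before the first interview.

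**What to change.** Reconcile the Appendix 3 guide with section 3.2.1 and Table 1:

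1. Replace the lead-in with one that fits a Week 8 visit. It should say that training was about seven to eight weeks ago and that the first questions concern the four weeks in which the parent kept the log.
2. Ask at least 3a to 3c in two labelled blocks. The first covers the four intervention weeks, with the parent's own log at hand. The second covers the weeks since, opening with whether Reiki was continued and, if so, how it was used.
3. Have coders tag each statement on use with its block, so that only Weeks 1-4 material is read against the log.

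The second block would also give a labelled account of use in Weeks 5-8, for which no log is planned.

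The cost is revised guide wording and a few extra minutes per interview. No visit, sample or instrument is added. If the guide is treated as part of the protocol, the revision goes to the IRB as a modification under section 6.3.
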